#### 4.3 Safety Endpoints

- Incidence and severity of all Adverse Events (AEs), Serious AEs (SAE), and Events of Special Interest (EOSI) pre-established in Section 6.7.1 of the protocol (including but not limited to Infections, Autoimmunity, Malignancies and Injection site reactions)
- Incidence and severity of clinically significant changes in vital signs
- Incidence and severity of clinically significant electrocardiogram (ECG) abnormalities
- Incidence and severity of clinically significant abnormalities in general laboratory tests

#### 4.4 Pharmacokinetic Endpoints

Through: Trough level serum concentration of BMS-931699 at time points specified in Section 5.5 of the protocol.

#### 4.6 Immunogenicity

Proportion of subjects with BMS-931699 induced antibody response over the time period for which samples are collected (specified in Table 5.5.3 of the protocol).

#### 5 SAMPLE SIZE AND POWER

The sample size calculation is based on power to compare the proportion of subjects who achieve BICLA response (the BICLA response rate) at Day 169 between each BMS-931699 dose arm and the placebo arm. With a one-sided continuity corrected chi-squared test at significance level 0.05, data from 70 treated subjects per arm will provide at least 89% power to detect a 25% increase in the BICLA response rate in the active treatment arm (i.e.. 50% response rate in BMS active arm) compared to placebo and provide 74% power to detect 20% increase in the BICLA response rate in the active treatment arm (i.e., 45% response rate in BMS-931699 arm) compared to placebo, assuming that the placebo arm has 25% response rate which is reasonable based on the EMBLEM phase 2 trial result. No adjustment will be made for multiplicity.

The primary efficacy analysis will be conducted on all randomized patients who received at least one dose of the study drug. In order to get 70 treated subjects per arm, an adequate numbers of subjects need to meet the inclusion/exclusion criteria at screening.

If the interim analysis for futility and dose adaptation suggests an additional dose arm at a lower dose level needs to be added, then up to 40 additional subjects may be randomized.

## **6 STUDY PERIODS, TREATMENT REGIMENS AND POPULATIONS FOR ANALYSES**

### **6.1 Study Periods**

The following periods are defined in this SAP for the purpose of analyses and reporting.

**Pre-treatment period:** It covers the time period which starts from the day of enrollment and lasts until the initiation of the randomized double-blind treatment period.

**Short-term period (ST):** It starts at the time of the first dose of blinded treatment (BMS-931699 or placebo, regardless if it was received during Part 1 or Part 2 of study design) and continues up to the start of the first long-term extension dose (Day 169). For subjects who discontinue during the short-term period or do not enter the long-term extension period, it continues up to 42 days post last dose.

**Long-term extension period (LTE):** It starts at the first dose date of long-term extension (Day 169) and continues up to 42 days post the last study dosing date (LTE dose). Cutoffs may be applied for interim locks.

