Short-term Period: 28 days (4 weeks) of screening, 168 days (24 weeks) of treatment, 42 days (6 weeks) of safety follow-up, for a total of approximately 238 days (34 weeks). Subjects randomized into either Part 1 or Part 2 will be treated for up to 24 weeks and will have the same procedures performed and will follow the same visit schedule. If subject is eligible and opts to continue into LTE, the 42-day follow-up visit will not be performed after the short-term period is completed and subject will enter LTE directly. If subject opts not to enter LTE then a follow-up visit will be completed 42 days after end of treatment. At the time of writing there is no defined end date to the long-term extension period, however, the LTE provision may be further adjusted based on results from the ongoing lulizumab development program. Subjects discontinuing treatment during the LTE period will complete the follow-up visit approximately 6 weeks after receiving their last dose of study medication.

Number of Subjects:

Approximately 450 subjects will need to be screened to randomize approximately 350 subjects. Utilizing a 1:1:1:1:1 randomization scheme resulting in approximately 70 subjects in the each treatment arm. If the day 85 interim analysis suggests an additional dose arm at a lower dose level needs to be added, then up to 40 additional subjects may be randomized.

Approximately 125 sites will participate in this study, which will be conducted globally and should include, but will not be limited to, participation of countries located in North America and Europe.

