All Investigator sites within this study will use an Electronic Data Capture (EDC) tool to submit study data to BMS. Electronic Case Report Forms (eCRFs) will be prepared for all data collection fields at Investigator sites, except for fields specific to Pregnancy Forms. Pregnancy Forms will be submitted to BMS using paper CRFs. Subject Quality of Life Questionnaires will be completed by the subject and the information will then be entered with the EDC tool by the investigational site staff. Physician Global Assessment of disease activity worksheet will be completed by the investigator and will then be entered with the EDC tool. Subject completed Quality of Life Questionnaires will be retained at the investigational site.

Study supplies and documents (eg, electronic Case Reports Forms, patient drug logs, etc.) will be provided to the study center by BMS. Urine pregnancy test kits, laboratory specimen collection kits and instructions for collection will be provided by central laboratory vendor. IVRS worksheets and instruction manuals will be provided by the IVRS vendor.

5.3 *Safety Assessments*

On Day 1, the results of all assessments must be reviewed to assure that eligibility requirements are met before contacting the Central Randomization System for the subject's randomization assignment.

Subjects who discontinue from the double-blind treatment period should have “End of Treatment Visit” procedures performed and should return to the clinical for the “Follow-Up Visit” approximately 42 days after the “End of Treatment Visit”. All procedures required for these visits should be completed as well as collection of concomitant medication information.

All assessments should be performed or administered prior to study drug administration unless otherwise indicated. Furthermore, patient’s assessments (ie FACIT-F, SF-36 and Subject’s Global Assessment) must be performed prior to all other assessments.

Every effort must be made to ensure the same evaluator will complete the assessments for each subject at all visits.

Only data for the procedures and assessments specified in this protocol should be submitted to BMS on a case report form. Additional procedures and assessments may be performed as part of your institutional or medical practice standard of care; however, data for these assessments should remain in the subject’s medical record and should not be provided to BMS, unless specifically requested from the sponsor.

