### **7.6            *Safety***

Analysis of all safety data will follow the BMS standard safety data conventions  and supplements to the standard conventions as defined in this document.

The evaluation of drug safety is based primarily on clinical AE, laboratory abnormalities and vital signs reported during the study.

The summaries of AEs and laboratory marked abnormality during the ST period will be provided by treatment groups. AEs and laboratory marked abnormalities will be included in the summary tables based on ST period if the onset date is on or after the first dose date and event occurs

within the ST period for continuing subjects or within 42 days post last dose date for discontinued subjects.

Frequency distribution and individual listings of all AEs will be generated. Laboratory marked abnormality using pre-defined abnormality criteria will also be descriptively summarized. There will be no statistical testing of group difference with respect to frequencies of AEs or laboratory marked abnormalities.

All recorded adverse events will be listed and tabulated by system organ class, preferred term, treatment and overall. Any physical examination findings will be listed. ECG, vital signs and clinical laboratory test results and corresponding change from baseline values will be listed and summarized by treatment. Values for ECG, vital signs and clinical laboratory test results outside the pre-specified criteria will also be listed and summarized. ECG readings will be evaluated by the Investigator and abnormalities, if present, will be listed.

Unless otherwise specified, baseline is defined as the last non-missing result with a collection date-time less than the date-time of the first dose of study medication, for laboratory results, vital signs and ECG.

Presentations for the ST period will be provided by “as treated” treatment group for the as-treated analysis population, unless otherwise specified.

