### **7.6.1 Adverse Events**

The investigator will determine the intensity of each AE as mild, moderate, severe, or very severe. In addition, the investigator will determine the relationship of the AE to the administration of the study drug.

All AEs are coded and grouped into Preferred Terms (PT) by System Organ Class (SOC), using the latest approved version of the Medical Dictionary for Regulatory Activities (MedDRA) at the time of database lock. Listings and summaries will be based on the resulting SOCs and PTs.

AEs will be included in the frequency tabulations if they occur while a subject is on study medication up to and including 42 days after the last dose of study medication. These AE summaries will be based on proportions, which represent the number of subjects experiencing the AEs divided by the number of subjects received with at least 1 dose of study medication in the current period.

All AE listings will indicate the unique subject identifier, age, gender, current treatment, the date of onset, the date of resolution, day of onset relative to the start of treatment, action taken, investigator’s assessment of severity and relationship to study drug. Additional listings will be provided for adverse events leading to discontinuation and adverse events without recorded resolution. Summaries of adverse events will include adverse events, adverse events by intensity and adverse events by relationship.

Where a subject has the same adverse event, based on preferred terminology, reported multiple times in a single analysis period, the subject will only be counted once at the preferred terminology level in adverse event frequency tables.

Where a subject has multiple adverse events within the same system organ class in a single analysis period, the subject will only be counted once at the system organ class level in adverse event frequency tables.

When a subject has the same adverse event, based on preferred terminology, reported multiple times in a single analysis period, the following criteria, in order of precedence, will be used to select the event to be included in summary tables:

- Relationship to study medication
- Intensity of event
- Onset date and time

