When reporting adverse events by intensity, in addition to providing a summary table based on the event selection criteria detailed above, summary tables will also be provided based on the most intense event during the analysis period - independent of relationship to study medication. For these tables, the following criteria, in order of precedence, will be used to select the event to be included in summary tables:

- Intensity of event
- Onset date and time

Subjects will only be counted once in the 'Total' at their maximum intensity, regardless of SOC or PT.

Any reported AEs that occur more than 42 days after the last dose of study drug will be excluded from safety summaries. Any reported AEs that occur more than 42 days post the last dose of study drug will appear in the listing.

Summary information (the number and percent of subjects by treatment) will be tabulated for the following AEs:

- All AEs including clinical and laboratory AEs
- Most common AEs (reported in 5% of subjects or more in any treatment group)
- All related events
- Serious AEs (SAEs)
- Discontinuations due to AEs

Laboratory AEs are laboratory changes identified by the investigator as AEs and thus reported on the AE pages of the eCRF.

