### **7.6.7 *Summaries of Laboratory Data***

The results of all protocol-specified clinical laboratory tests, as well as laboratory results outside of the normal range, will be listed. Scheduled laboratory measurements and corresponding change from baseline values will be summarized by treatment and nominal visit for each laboratory test for the MITT analysis population.

The frequency of subjects with any marked laboratory abnormality (based on sponsor defined criteria) will be presented by laboratory test during the ST period. The results are based on the As-treated analysis population. The criteria used for classifying laboratory test results as markedly abnormal will be listed.

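### Follow-up Day 42 is timed from end of treatment in some places and from last dose in others; on the first reading a completer's visit falls about day 49, outside the SAP's 42-day safety tables

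*SAP*

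**What the plan says.** **The visit.** By the footnote to Protocol Table 5.1-2, the visit applies only to subjects who stop early or who complete 24 weeks without entering the long-term extension (LTE). Safety laboratory tests are drawn at it (same table). Its timing is given in two ways.

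- *From EOT.* The synopsis, Protocol 3.1 and SAP 2.1 state: "If subject opts not to enter LTE then a follow-up visit will be completed 42 days after end of treatment". Protocol 5.3 places the visit of discontinuing subjects "approximately 42 days after the" End of Treatment Visit. Table 5.5.3 counts the follow-up PK and immunogenicity samples from EOT as well.
- *From last dose.* This is the anchor in the schematic notes of both documents, in the paragraph on discontinuing subjects in Protocol 3.1 and SAP 2.1, and in SAP 7.9.

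**The tables.** SAP 6.1 ends the short-term period for subjects who discontinue or "do not enter the long-term extension period, it continues up to 42 days post last dose". For LTE entrants the period "continues up to the start of the first long-term extension dose (Day 169", which makes the Day 169 injection an LTE dose. SAP 7.6 admits adverse events and marked laboratory abnormalities "within 42 days post last dose date for discontinued subjects". SAP 7.6.1 counts adverse events "up to and including 42 days after the last dose of study medication" and adds: "Any reported AEs that occur more than 42 days after the last dose of study drug will be excluded from safety summaries". Those later events stay in the listing. SAP 7.6.7 says the frequency of subjects with "any marked laboratory abnormality (based on sponsor defined criteria) will be presented by laboratory test during the ST period", so that table takes its limit from 6.1.

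**The concern.** A table limit counted from last dose fits a visit counted from last dose. It does not fit a visit counted from EOT, because in a completer EOT comes one dosing interval after the last injection. The sentence written specifically for completers who decline the LTE uses EOT. Followed as written, it puts their only scheduled post-treatment laboratory draw beyond the limit of the marked-abnormality table.

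What is at stake is the tabulation of late safety findings, and whether sites work to one schedule. For discontinuing subjects, Protocol 3.1 (last dose) and Protocol 5.3 (End of Treatment Visit) contradict each other directly.

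**Working it through.** **Inputs**

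- Weekly injections from Day 1 (Protocol 4.5.1); dosing interval 7 days (SAP 7.4.1).
- EOT on Day 169, entered as 168:00 hours after dose (Table 5.5.3).
- A Day 169 injection belongs to the LTE (SAP 6.1).
- Windows of ±2 days for visits (Table 5.1-2) and for doses (Protocol 4.5.1.1).
- Half-life 7 days (Protocol 3.3.1). Check: 5 × 7 + 30 = 65 days, the stated contraception period for women.

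**Last injection of a completer who declines the LTE.** There are 24 weekly injections, the last on Day 1 + 7 × 23 = Day 162. EOT is 169 − 162 = 7 days later, which agrees with 168:00 hours.

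**The plan's own duration.** The stated approximate total is 28 + 168 + 42 = 238 days (34 weeks).

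- EOT timing: visit on Day 169 + 42 = Day 211, which is 210 days after Day 1; 28 + 210 = 238 days. This matches.
- Last-dose timing: visit on Day 162 + 42 = Day 204, which is 203 days after Day 1; 28 + 203 = 231 days (33 weeks). This does not match.

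**Visit against the table limit (last injection + 42 days = Day 204)**

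| Anchor | Visit, days after last injection | With ±2 on the visit | Days past the limit |
|---|---|---|---|
| EOT | 211 − 162 = 49 | 47-51 | 7 (5-9) |
| Last dose | 204 − 162 = 42 | 40-44 | 0 (at most 2) |

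With the windows for last dose, EOT and follow-up stacked, the EOT-timed visit falls between (167 − 164) + 40 = 43 and (171 − 160) + 44 = 55 days after the last injection. It is past the limit throughout.

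Discontinuing subjects have no scheduled gap between last dose and EOT, so no figure can be given for them.

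**Drug remaining,** assuming first-order elimination, 0.5^(t/7):

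- Weekly arm, from Day 162: 0.5^6 = 1.6% at Day 204 and 0.5^7 = 0.8% at Day 211.
- Every-other-week arms, if active drug is given first: the last active dose is Day 1 + 14 × 11 = Day 155. Day 204 is then 49 days later (0.8%) and Day 211 is 56 days later (0.5^8 = 0.4%).

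**The case against.** **The 42-day limit may be a deliberate risk window.** Amendment 06, item 53, explains the 42-day limit for collecting serious adverse events by the drug's half-life and the estimated receptor occupancy, as well as by consistency with the schedule of visits. A window for treatment-emergent events need not contain every visit. This stands in part: 42 days has a pharmacological basis, so the 42-day table is worth keeping. But alignment with the visit was also a stated reason, and Table 5.1-2 extends serious-event collection to the last scheduled visit if that is later. The SAP tables do not follow.

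**Little drug is left by then.** This stands, and more so in the three every-other-week arms if active drug comes first. The post-dose PK days in Table 5.5.3 suggest that order: they follow Days 43, 57 or 71, each a multiple of 14 days after Day 1.

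**The stated duration favours EOT.** This stands. Choosing last dose means changing the 238-day figure and moving a visit, which is more than tidying words. The duration is labelled approximate, so it supports the EOT reading without settling it.

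**The Day 169 dose is not described uniformly.** Protocol 8.7.1 starts the LTE with a dose after Day 169, and the synopsis equates 24 weeks with 169 days. If a short-term injection were given on Day 169, the two anchors would coincide. The 168:00 entry and SAP 6.1 both point against that. The claim that the EOT-timed visit is always outside the tables also assumes that the windows are kept; Protocol 5.3 says only that the interval is approximate.

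**Stronger readings.** A reader might infer that late safety findings disappear from the report. They do not: late adverse events are listed, all protocol-specified laboratory results are listed, and SAP 7.6.7 also summarizes scheduled values by nominal visit without stating a 42-day limit there. A reader might also infer a bias between arms. The documents give no basis for one: the same visit schedule and cut-off apply in every arm.

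**Conclusion.** The conflict is real and minor. It is a clash between stated rules, so more detail elsewhere would not resolve it. For a completer who declines the LTE, the EOT-timed visit falls 49 days after the last injection, 7 days past the limit. A marked laboratory abnormality first measured there misses the frequency table, and adverse events with onset from day 43 to the visit are listed but not tabulated. Events with onset by day 42 still count, even if first reported at the visit. With last-dose timing, only a visit on day 43 or 44 is affected.

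LTE entrants skip this visit at the end of the short-term period and are unaffected there. The primary endpoint is untouched. The number of affected subjects cannot be derived from the documents. The result rests on a last injection on Day 162, as SAP 6.1 and Table 5.5.3 imply. The change is desirable rather than essential.

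**What to change.** Name one anchor and match the table cut-off in SAP 6.1, 7.6 and 7.6.1 to it; 7.6.7 then follows through 6.1.

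- **(a) Last dose throughout.** Amend the synopsis, Protocol 3.1 and 5.3, Table 5.5.3 and SAP 2.1. Set the cut-off at 44 days after last dose, and restate the short-term duration as about 231 days. For completers the visit, with its PK and immunogenicity samples, moves a week earlier, and sites must be told.
- **(b) EOT.** This keeps the 238 days. Align the schematic notes, the text on discontinuing subjects and SAP 7.9. Set the cut-off at 51 days after last dose, or 55 to cover stacked windows. Keep the 42-day table as a supplementary display, since 42 days also rests on half-life and receptor occupancy. If discontinuing subjects stay on the last-dose anchor, the tables will cover some time beyond their follow-up.

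Neither option adds a procedure. The cost is protocol and SAP wording, plus the moved visit under (a), and a slightly longer risk window with little drug left. In that window a few tabulated events would be less likely to be drug-related.

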### **6.2 Treatment Regimens**

All subjects will receive BMS-931699 or Placebo every week (double-dummy).

- BMS-931699 at 12.5mg weekly sub-cutaneous (SC) injection
- BMS-931699 at 12.5mg every other week (EOW) SC injection
- BMS-931699 at 5mg EOW SC injection
- BMS-931699 at 1.25mg EOW SC injection
- Placebo SC injection (every week)

Subjects randomized to weekly subcutaneous injections of either placebo or BMS-931699 will be dosed weekly as per schedule and subjects randomized to one of the every other week arm will be alternating between receiving a subcutaneous injection of BMS-931699 one week and one of placebo the following week.

There may be an instance of new treatment group as per study design. Also one or more treatment arms (other than Placebo) may be dropped based on interim analyses.

For more details, see study design in IM128-027 Protocol.

### **6.3 Populations for Analyses**

- All Enrolled Subjects: All subjects who signed an informed consent.
- All Randomized Subjects: All subjects who are randomized to a treatment.

- Modified Intent-to-Treat (MITT) Analysis Population: All randomized subjects who have received at least one dose of the study medication. Subjects will be grouped according to the treatment to which they were randomized by IVRS at the start of the study. The MITT analysis population will also be referred to as “All Randomized and Treated Subjects”.
- As-Treated Analysis Population: All Subjects who have received at least one dose of study medication. Subjects will be grouped according to the treatments to which they are randomized, except in cases where a subject receives a different treatment for the entire course of short term period. In this case, the subject will be analyzed and presented by the treatment they actually received.
- Efficacy Analysis Population: This is a subset of the MITT Analysis Population where the subjects from Part 1 who are randomized to a treatment arm and discontinued based on the Part 1 Safety/RO analysis are excluded. All efficacy results that involve statistical comparison or modeling will be based on this analysis population unless otherwise specified.
- Biomarker Analysis Population: All subjects who receive any study medication and have at least one post-treatment biomarker measurement.
- Pharmacokinetic Population: All subjects who received BMS-931699 and have any available concentration-time data.
- Immunogenicity Population: All subjects who receive any study medication and have at least one post treatment immunogenicity assessment.

